**Reporting Adverse Events (AE) and Serious Adverse Events (SAE)**

**Anticipated Adverse Events:** Anticipated adverse events in this study include Purpura, blistering, bruising, bullae, erosion, soreness and burn. If an unanticipated adverse event occurs at any time during or after the use of the SlimShape device, the Investigator must report it to Syneron.

The Investigator must report all unanticipated adverse device effects that are serious in nature to the clinical study monitor immediately or within twenty-four hours by telephone (see below). If such an unanticipated adverse device effect is reported after normal working hours, the Investigator will leave a voice message at the monitor's telephone number with accompanying report of the unanticipated adverse device effect faxed or sent to the fax number/e-mail address below:

 Syneron Medical Ltd. Confidential	Clinical Study to Evaluate the Safety and Efficacy of the SlimShape Device for Abdominal Fat and Circumference Reduction			
	Protocol #	DHF22621	Rev. Date	October 8, 2017

[name], Global VP of Clinical Affairs  
Telephone/Fax No.: From the U.S. [name]  
[name] (cell)  
E-mail: [contact]

A written report prepared by the Principal Investigator must follow within five working days to both the IRB and to Syneron and should include a full description of the event and sequence.

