### **Anticipated Adverse Effects**

Following treatment with the *SlimShape* the following local adverse effects could occur (anticipated):

- Purpura
- Blister
- Bruising
- Bullae
- Erosion
- Pain/ soreness
- First degree burn
- Second degree burn

An adverse event (AE) is any undesired clinical occurrence in a study subject as indicated by signs, symptoms, illnesses, events that develop or worsen in severity in association with the study when deemed by the Investigator to be related to use of the device or study procedures. The Investigator will document all adverse signs and symptoms regardless of severity or frequency that are either volunteered by subjects or observed during the course of the study that are related to the device. The Investigator will also record adverse experiences of subjects resulting from concurrent illnesses, reactions to concurrent medications, or progression of disease states that the Investigator deems related to the device. Included in the description will be the nature of the sign or symptom, the date of onset, whether the event was serious, the severity, the relationship to study procedures or investigational device, the action taken, the date of resolution, and the outcome. The Principal Investigator will determine the relationship of the adverse device effect to the investigational device.

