### **Unanticipated Adverse Device Effects**

For device studies, part 21 CFR 812.3(s) uses the term unanticipated adverse device effect which is defined as any serious adverse effect on health or safety or any life-threatening problem or death caused by, or associated with the device, if that effect, problem, or death was not previously identified in nature, severity, or degree of incidence in the investigational plan or application (including a supplementary plan or application), or any other unanticipated serious problem associated with a device that relates to the rights, safety, or welfare of subjects.

 Syneron Medical Ltd. Confidential	Clinical Study to Evaluate the Safety and Efficacy of the SlimShape Device for Abdominal Fat and Circumference Reduction			
	Protocol #	DHF22621	Rev. Date	October 8, 2017

Significant device failure may constitute an adverse event if an undesirable experience occurs. This definition includes any event resulting from insufficiencies or inadequacies in the instructions for use or the deployment of the device, or any event that is a result of a user error.

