### **Monitoring Plan**

At least 3 monitoring visits are projected during the whole study. The frequency of which will be based on enrolment, study activities and the study visit scheduled. The first visit is scheduled at the initiation of the study prior to the first subject treatment in the study. The second visit is scheduled after enrolment and treatment has been initiated and a third visit will be for a close-out visit for the study. Interim visits may be conducted as needed to assure compliance to the study protocol and regulatory requirements. The number and frequency of monitoring visits may also be increased per the sponsor decision to collect data and images post treatment.

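### The only timed safety report covers serious, unanticipated device effects; serious events of a listed type or judged unrelated have no deadline, and the adverse-event definitions conflict

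*Combined protocol and SAP*

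**What the plan says.** In the protocol, *Reporting Adverse Events (AE) and Serious Adverse Events (SAE)* contains one duty with a time limit: "The Investigator must report all unanticipated adverse device effects that are serious in nature to the clinical study monitor immediately or within twenty-four hours". This notice is given by telephone and then followed up in writing: "A written report prepared by the Principal Investigator must follow within five working days to both the IRB and to Syneron". A second duty in the section has no time limit: "If an unanticipated adverse event occurs at any time during or after the use of the SlimShape device, the Investigator must report it to Syneron". It also lists what is expected: "Anticipated adverse events in this study include Purpura, blistering, bruising, bullae, erosion, soreness and burn". *Anticipated Adverse Effects* and *Risks* give a longer list that separates burns by degree and stops at "Second degree burn".

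Three definitions decide which events these duties reach:

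- *Unanticipated Adverse Device Effects* requires a serious effect with a link to the device that "was not previously identified in nature, severity, or degree of incidence in the investigational plan". It also takes in other unanticipated serious problems associated with a device.
- The opening of *Adverse Events (AE)* counts any worsening of health or side effect during participation.
- *Anticipated Adverse Effects* defines an adverse event again, this time only "when deemed by the Investigator to be related to use of the device or study procedures".

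The Glossary spells out SAE, but the body of the protocol does not define it.

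**The concern.** The section heading promises rules for serious adverse events in general, but the timed rule turns on whether the event was expected and whether it is a device effect. If a site follows the text, seriousness alone triggers no timed report. Treatment may be running at up to 10 sites while the sponsor has not heard of a serious event at one of them.

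The second stake is the primary safety endpoint, which covers adverse events of every kind. If events judged unrelated are never classed as adverse events, the count depends on each investigator's view of causality. In a one-arm study no control group would reveal that loss.

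**Working it through.** No arithmetic applies, because the point is about the scope of a rule. The check sets the sections side by side.

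**Step 1. Conditions for the timed report.** The 24-hour sentence needs three things together: serious, unanticipated, and a device effect. The five-working-day sentence comes directly after it, and I read it as following from the same trigger.

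**Step 2. Apply the duties to each kind of serious event.**

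| Serious event | 24-hour call and five-day written report | Untimed report to sponsor |
|---|---|---|
| Unanticipated, device effect | Yes | Yes |
| Anticipated type and degree, device effect | No | No |
| Unanticipated, judged unrelated | No | At most |
| Anticipated type and degree, judged unrelated | No | No |

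One class of four has a deadline. The third row says *at most* because the untimed duty has no relatedness condition of its own, but it applies to an adverse event, and under the narrower definition an unrelated event is not one.

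**Step 3. Where the anticipated boundary lies.** The reporting section lists burns with no limit of degree or seriousness. The longer list names first and second degree only. The definition of an unanticipated effect turns on nature, severity and incidence, so a burn beyond what the plan identified is unanticipated and falls under the 24-hour rule. What remains is a serious event within the listed types and degrees. The unqualified entry in the reporting section makes that line hard for a site to draw.

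**Step 4. Other routes to the sponsor.**

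| Section | Route | Deadline stated |
|---|---|---|
| *Protocol Revisions and/or Deviations* | Prompt report of emergency medical procedures | None; covers procedures, not serious events as such |
| *Study Monitoring/Auditing/Inspection* | Regular telephone and e-mail contact | None |
| *Case Report Forms* | Timely submission of adverse event forms | None |
| *Recording* | CRFs collected at monitoring visits | Depends on the visit schedule |

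On that schedule, *Monitoring Plan* says "At least 3 monitoring visits are projected during the whole study": one before the first treatment, one after treatment has begun, and one at close-out. More visits are allowed, but a serious event does not oblige one.

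**Step 5. Is every adverse event recorded?** The opening definition covers any adverse change, related or not. The relationship categories include *Probably not* and *Not related*, which have a use only if such events are recorded. *Primary Safety Endpoint* has no relatedness limit. Against these three stands the definition in *Anticipated Adverse Effects*, which admits only events deemed related. That section also asks for seriousness to be recorded, but attaches no expedited action to it.

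**The case against.** The strongest defence is that being on the list does not by itself make an event anticipated. *Risks* states that no serious or unanticipated events have been reported to date and that the events seen were all mild. A serious burn could then be read as exceeding the severity identified, which would bring it under the 24-hour rule. That reading is available and is clear for a burn beyond second degree. It is not clear for a serious second degree burn, because the plan names that degree as anticipated and sets no seriousness limit. A site deciding within a day should not have to settle this.

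A reader might infer three stronger claims that the documents do not support:

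- *Unrelated serious events have no route to the sponsor.* The untimed duty to report unanticipated events carries no relatedness limit, so on the broader definition an unexpected unrelated illness must be reported. What it lacks is a deadline.
- *A serious burn would only be written on a paper CRF.* The duties on adverse event forms, emergency procedures and regular contact contradict this. For the same reason, a delay until close-out is possible under the minimum visit schedule but is not what the protocol prescribes.
- *Burns are the events most likely to become serious with this device.* The documents give no data for that ranking. The burn serves here only as an example of a listed type.

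The ethics section commits the study to sponsor procedures, federal regulations and good clinical practice guidance, which may contain timelines. None is reproduced in the protocol, so they cannot be used here to supply the missing deadline.

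**Conclusion.** The point holds. The stated rule is too narrow: three of the four classes of serious event have no deadline for reaching the sponsor, and two of those three have no specific reporting duty in that section at all. The conflict between the adverse-event definitions is a separate defect, through which unrelated serious events may go unrecorded.

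The number of events affected cannot be estimated. The favourable history in *Risks* suggests few, and a confidence bound on an event rate in 120 subjects would say nothing about how fast a report travels. Nor can the delay be given in days, because the interval between monitoring visits is not fixed.

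The conclusion assumes that the five-day report belongs to the 24-hour notice and that no timeline outside these documents fills the gap. The protocol should be corrected because the matter concerns subject safety and the remedy is small.

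**What to change.** 1. Define a serious adverse event in the body of the protocol.
2. Amend the 24-hour sentence in the reporting section so that it and the five-working-day written report apply to every serious adverse event, whether or not anticipated and whether or not judged device-related. Keep unanticipated device effects as a named subset.
3. Reconcile the opening of *Adverse Events (AE)*, *Anticipated Adverse Effects*, *Unanticipated Adverse Device Effects*, the relationship categories and the reporting section, so that all adverse events are recorded and relatedness is an attribute of the record. Align the two lists on burn degree in the same edit.

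Step 2 alone would leave the narrow definition standing and would not protect the safety count, so step 3 is needed as well. The cost is a short text change, brief site training and a few more expedited reports.

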**Measures taken to protect the rights and welfare of subject**

Research records will be available to study personnel, the sponsor, Ethics Review Committee and regulatory agencies as required. Research records may be used for purposes of medical education, after removal of subject names or other identifying information. In the ICF the subjects will be informed that the photographs and video taken of them during the study may be made available to the sponsor for marketing and instructional purposes, after removal of identifying information. All images collected will be stored without personal subject identifiers at the site and at Syneron.

**RISK/BENEFIT ANALYSIS**

**Risks**

Syneron has determined that the *SlimShape* system is non-significant risk device. As indicated in the AE section, the anticipated risks associated with the use of both of the systems are:

- Purpura
- Blister
- Bruising
- Bullae
- Erosion
- Pain/ soreness
- First degree burn
- Second degree burn

Over 2500 subjects worldwide participated in clinical research and underwent treatment with the different *VelaShape family* devices. The *SlimShape* device will be used in this study was previously used in studies and emitted the same acoustic energy. To date, no serious adverse events or unanticipated AEs have been reported. The reported AEs relate to skin and subcutaneous tissue, confined to the treatment area and were all mild in nature and resolved within the study period.

**Potential benefits to participating individuals and to society**

Subjects may or may not benefit from reduction of subcutaneous fatty tissue on the treated area via a non-invasive technique resulting in body contouring improvement. All subjects in the treatment groups are expected to have some benefit from the treatment procedures as would

 Syneron Medical Ltd. Confidential	Clinical Study to Evaluate the Safety and Efficacy of the SlimShape Device for Abdominal Fat and Circumference Reduction			
	Protocol #	DHF22621	Rev. Date	October 8, 2017

be expected for the commercial devices (*SlimShape*). Subject will receive all treatment procedures at no cost. This study will benefit the advancement of medicine by generating data on safety and efficacy that will aid in the development of an alternative treatment options to procedures with higher potential risks subjects, such as liposuction. The results of this study will help to determine whether this device is safe and effective for improvement of localized subcutaneous fat.

**Conclusion:**

In light of the potential benefits of non-invasive body contouring relative to its risks, the potential benefits associated with the use of the SlimShape System outweigh its risks, supporting study initiation.

**ETHICS AND GOOD CLINICAL PRACTICE**

This study will be carried out in compliance with the following:

- Syneron Standard Operating Procedures.
- Declaration of Helsinki, concerning medical research in humans (Recommendations Guiding Physicians in Biomedical Research Involving Human Subjects, Helsinki 1964, amended Tokyo, 1975, Venice 1983, and Hong Kong 1989).
- US Code of Federal Regulations (Title 21CFR including parts 50, 56 and 812 governing informed consent and IRB regulations).
- International Conference on Harmonization (ICH) Harmonized Tripartite Guideline for Good Clinical Practice (GCP), 1996.

**QUALITY ASSURANCE AND STUDY MONITORING**

**Study Monitoring/Auditing/Inspection**

The Study Monitor will be responsible for monitoring the study sites to review the data being collected. The sponsor shall implement and maintain quality control and quality assurance procedures with written standard operating procedures (SOPs) to ensure that the trial is being conducted and data are generated, documented and reported in compliance with the protocol, Good Clinical Practice (GCP) and applicable regulatory requirements. Visits will be made prior to the initiation of the study, at scheduled intervals throughout the study, and at termination of the study.

Once enrollment and treatments have begun, monitoring visits will take place more frequently pending enrollment and study activities.

 Syneron Medical Ltd. Confidential	Clinical Study to Evaluate the Safety and Efficacy of the SlimShape Device for Abdominal Fat and Circumference Reduction			
	Protocol #	DHF22621	Rev. Date	October 8, 2017

The sponsor and site will maintain regular phone and e-mail correspondence throughout the study to confirm compliance of study procedures.

The investigator/institution agrees to allow the monitor and other authorized personnel direct access to source data/ documents for trial related monitoring, the clinical supplies storage/dispensing area and to provide all documents in the Investigator Regulatory Binder for review, and to assist site auditors in their activities if requested. Requests by the Health Canada or regulatory agencies of other countries to inspect the study site may be made after adequate notification. The investigator may be required to assist the regulatory inspectors in their duties, if requested.

## **ADMINISTRATIVE PROCEDURES**

### **Supply and Disposition of Study Device**

The *SlimShape* device and VelaEase (coupler agents) will be supplied to the participating clinic. The device will be maintained by the Sponsor, as needed. Unused equipment or coupler agents will be returned to the sponsor at the end of the study. At the end of all planned treatment sessions the devices will be returned to Syneron.

### **Control & Disposition of the Investigational Device**

The *SlimShape* device will be used according to the instructions of the Sponsor and manufacturer, Syneron Medical. At the end of this study, any materials provided specifically for use in this study may be returned to the Sponsor, as described in the Clinical Trial Agreement and study budget.

### **Informed Consent**

The Study Personnel will obtain written Informed Consent prior to the subject's participation in any study procedures. The Study Personnel will inform the subjects of the experimental procedure to be utilized and assure the subjects that their decision regarding participation in the study will have no bearing on the quality of medical care received and that their decision whether to participate in the study is strictly voluntary.

During the initial interview, the subject will be assured that they are free to change their mind and will be allowed to participate in the study or withdraw from the study with no adverse effect on their standard medical care.

 Syneron Medical Ltd. Confidential	Clinical Study to Evaluate the Safety and Efficacy of the SlimShape Device for Abdominal Fat and Circumference Reduction			
	Protocol #	DHF22621	Rev. Date	October 8, 2017

### **Monitoring Plan**

At least 3 monitoring visits are projected during the whole study. The frequency of which will be based on enrolment, study activities and the study visit scheduled. The first visit is scheduled at the initiation of the study prior to the first subject treatment in the study. The second visit is scheduled after enrolment and treatment has been initiated and a third visit will be for a close-out visit for the study. Interim visits may be conducted as needed to assure compliance to the study protocol and regulatory requirements. The number and frequency of monitoring visits may also be increased per the sponsor decision to collect data and images post treatment.

### **Case Report Forms**

Paper case report forms will be used in this trial. All protocol-required information collected during the study must be entered in the appropriate field of the case report form (CRF). The investigator, or designated representative, should complete the appropriate CRF fields as soon as possible after information is collected. The information must match the information that exists as source documents in the clinic chart, hospital chart, and/or investigator's files. An explanation should be given for all missing data.

It is the investigator's responsibility to assure the accurate completion, review, and approval of all CRFs and the timely completion and submission of all adverse event forms.

### **Record Maintenance**

The investigator shall retain a copy of all study documents in accordance with the FDA regulations which specify that records should be kept for a period of two years: 1) following the date a marketing application either is approved or disapproved for the use, or 2) following notification to FDA that no application is being filed and/or that the study has been discontinued.

If an investigator leaves the study site before record retention obligations have expired, the sponsor should be notified in writing of the person designated to retain the study documents during and after the study.

*Handling of clinical data.* The data are entered into a secure database that only the sponsor has access to. Admission to the database requires access to a password-protected network secured by the Sponsor. This database is maintained by Syneron that performs backups, data verification, and application upgrades. All equipment housing the clinical data is located in locked rooms or a secure computer network. The only individuals, who view, extract and analyze data for protocol reports and publications are physicians and nurses who are members of the study team or Sponsors. Only authorized personnel of the Sponsors have access to databases.

Any paper copies of subject medical records or research records are stored in secure cabinets at the study site.

 Syneron Medical Ltd. Confidential	Clinical Study to Evaluate the Safety and Efficacy of the SlimShape Device for Abdominal Fat and Circumference Reduction			
	Protocol #	DHF22621	Rev. Date	October 8, 2017

**PUBLICATION POLICY**

The investigator will not publish the study results and will not disclose confidential information received from Syneron without prior written agreement from Syneron. Such confidential information shall include any and all information relating to this study as described in the Clinical Trial Agreement. In the event that Syneron consents to the publication of data from this study, the investigator will provide Syneron manuscripts for review thirty days before submission for publication. Syneron will have no editorial rights over manuscripts. The investigator will also provide Syneron with advance notice of at least (30) days, of any presentation, lecture, abstract session, etc., in which any results from the study will be disclosed.

 Syneron Medical Ltd. Confidential	Clinical Study to Evaluate the Safety and Efficacy of the SlimShape Device for Abdominal Fat and Circumference Reduction			
	Protocol #	DHF22621	Rev. Date	October 8, 2017

